### 8.3.1.12 Work Productivity Survey (WPS)

The WPS is a 9 question instrument used to assess the impact of arthritis on productivity within and outside the home during the preceding 4 weeks. One of the WPS questions concerns the employment status, 3 relate to work productivity outside the home, and 5 ask about household work and daily activities. Subjects employed outside the home will be asked questions about the number of work days missed due to arthritis, the number of days with productivity at work reduced by half or more due to arthritis, and the interference of arthritis on work productivity on a 0 to 10 scale (0=no interference; 10=complete interference). In addition, all subjects regardless of their employment status will be asked questions about the number of household work days missed due to arthritis, the number of days with productivity in household work reduced by half

or more, the number of family, social, or leisure activities days missed due to arthritis, the number of days with outside help hired due to arthritis, and the interference of arthritis on household work productivity on a 0 to 10 scale (0=no interference; 10=complete interference).

In order to make data consistent and amenable to statistical analysis, the following counting rules will be applied to handle out of range and ambiguous answers of the WPS.

These counting rules will be applied prior to conducting any type of statistical analysis of the data.

### WPS counting rules

Due to the inter-relation between certain questions of the WPS, the priority order for implementing these specific counting rules is as in the listed order below.

#### WPS Question 1 (Q1) (employment status)

- If (Q1=missing) and (Q2>0 or Q3>0 or Q4>0), then Q1=YES.
- If (Q1=missing) and {(Q1.a (1) is not missing) or (Q1.a (2) is not missing)}, then Q1=YES.
- If (Q1=missing) and (Q1.b is not missing), then Q1=NO.

For all rules below, the original value will be kept and displayed in the listings but the corrected value will be considered for the analyses (tables).

- If employment status="No" and Job function is not " " then Job function=" ".
- If employment status="No" and occupation is not " " then occupation=" ".
- If employment status="Yes" and subject's status is not " " then status=" ".

#### WPS Q2 (missed work days due to arthritis)

- If (Q1=NO), then Q2="." (missing)
- If Q2 =0 or missing (.) and if Q1 (Employment Status) is Missing (.) then Q2=. (replace 0 by ".").

#### WPS Q3 (days with reduced productivity at work by half or more due to arthritis)

- If (Q1=NO), then Q3="." (missing).
- If Q3 =0 or missing (.) and if Q1 (Employment Status) is Missing (.) then Q3=. (replace 0 by ".").

#### WPS Q4 (rate of arthritis interference on work productivity (work outside of home))

- If (Q1=NO), then Q4="." (missing).
- If Q4 is out of range, then Q4="." (missing).
- If Q4=0 or missing (.) and if Q1 (Employment Status) is Missing (.) then Q4=. (replace 0 by ".").

#### WPS Q9 (rate of arthritis interference on household work productivity)

- If Q9 is out of range, then Q9="." (missing).

## WPS Q2 to Q9

For the rule below, the original value will be kept and displayed in the listings but the corrected value will be considered for the analyses (tables).

- If value=X.5 then value=X+1 (for ex: 1.5->2).

With regards to missing observations at Baseline, the following rules apply:

- Q1 (categorical): missing Baseline is not imputed
- Q2-Q9 (discrete): missing Baseline is imputed by the mean of the available subjects, rounded to the closest integer.

For WPS, the following correction rules have to be applied for Q1, Q2, Q3 and Q4 prior to any analysis of the data to make the data consistent and amenable to statistical analysis:

If Q1='No' and Job function is not ' ' then Job function=' '.

If Q1='No' and occupation is not ' ' then occupation=' '.

If Q1='Yes' and subject's status is not ' ' then status=' '.

If Q1='No' and Q2 is not missing, then Q2='.'

If Q1='No' and Q3 is not missing, then Q3='.'

If Q1='No' and Q4 is not missing, then Q4='.'

### 8.3.1.13 Medical Outcomes Study (MOS) sleep scale

The MOS Sleep Scale is a validated generic self-administered scale measuring specific aspects of sleep. The frequency with which each problem has been experienced during the previous 4 weeks is rated on a 5-point scale ranging from "none of the time" to "all of the time", except sleep quantity, which is reported in hours. All scores are transformed linearly to range from 0 to 100, again with the exception of the sleep quantity subscale, which is scored in hours. Higher scores indicate more of the attribute implied by the scale name (eg, more sleep disturbance, more adequate sleep, or greater sleep quantity).

QualityMetric Health Outcomes™ Scoring Software will be used to calculate the domains of Sleep disturbance, Snoring, Sleep short of breath or headache, Sleep adequacy, Sleep somnolence, Sleep problems Index I, Sleep problems Index II.

### 8.3.1.14 Health Status (EQ-5D)

The EQ-5D consists of a 5-item health status measure and a VAS. Each of the 5 health states is divided into 3 levels (no problem, some or moderate problems, and extreme problems) and is scored as 1, 2, and 3, respectively. The EQ-5D VAS records the respondent's self-rated health status on a vertical 20cm scale, 0 to 100 graduated (0=worst imaginable health status, 100=best imaginable health status).

The VAS will be evaluated by changes from Baseline and actual scores. The 5 dimensions will be analyzed categorically.

As electronic data capture is being used, ambiguous and out of range answers are not expected. However, if these rules are needed, see Appendix 13.2.

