#### **4.2.3 Other efficacy variables**

For the analysis of the double-blind 52-week treatment period, other binary efficacy variables will be treated in the same way as the primary analysis of the primary efficacy variable (composite endpoint). That is, a subject will be considered a responder only if the response is achieved and if the subject is still on their randomized double-blind study treatment at the time

when the variable is evaluated. Analyses of other continuous efficacy variables will be based on LOCF. A sensitivity analyses will be performed on all other efficacy variables using observed case analysis as described for the primary endpoint in [Section 4.2.1](#).

For analysis of the Week 156/SFE-WD visit data, binary efficacy variables will be analyzed using the non-responder imputation (NRI) approach; that is, where the denominator is all subjects in the SFE-FAS for the given treatment group. A subject will be considered a responder only if the response criterion of the given variable is achieved. All other subjects will be counted as not responding e.g. subjects who have not achieved the given outcome and all subjects with missing data are set to non-response.

An observed case analysis of binary efficacy variables at Week 156/SFE-WD will be performed. The Observed Case analysis at Week 156, will consider a subject a responder only if the response is achieved. Non-response at Week 156 visit will be counted as non-responders. Early withdrawals or subjects with missing data will be considered missing in this analysis. The sensitivity analysis of the Observed Case analysis at Week 156/SFE-WD will consider a subject as a responder if response is achieved at Week 156/SFE-WD visit such that both subjects with a Week 156 visit (subjects who complete) and subjects with early withdrawal visits and efficacy results meeting the criteria of response, will be counted as a responder. Subjects with missing data will be considered missing in this analysis.

For continuous efficacy variables, the observed data at Week 156/SFE-WD visit will be analyzed. This will summarize efficacy data for completers and subjects with early withdrawal visits during SFE together. In addition, the efficacy data collected at Week 156 for completers only will be summarized.

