### 8.3 Analysis of other efficacy variables during the double-blind 52-week treatment period

The efficacy analyses described in this section are not part of the multiplicity-controlled testing procedure described in [Section 8](#). The p-values reported for these analyses will not be adjusted for multiplicity and will be considered nominal. Derivations for these other efficacy variables can be found in [Section 8.3.1](#).

Continuous other efficacy variables will be analyzed using an ANCOVA model including Baseline score as a covariate, and fixed effects for treatment group, region, and MRI/CRP classification. The treatment differences and corresponding 95% CIs will be calculated based upon the adjusted least squares means. Missing values or values observed after discontinuing the double-blind study treatment will be imputed using LOCF. In addition, as described in [Section 4.2.3](#), an observed case analysis will also be performed for subjects still on the original double-blind study treatment. Tables for continuous variables will display descriptive statistics for Baseline, absolute values and change from Baseline at post-Baseline time points.

Categorical other efficacy variables will be analyzed using a logistic regression model with factors of treatment group, region, and MRI/CRP classification (MRI+/CRP+; MRI+/CRP-; MRI-/CRP+). If the logistic regression model is unable to converge, then the MRI/CRP classification variable may be dropped from the model to facilitate convergence. Tables for the binary variables will display the responder rates for the various time points. Analyses will be presented in 2 ways (as described in [Section 4.2.3](#)). First, they will be presented where the denominator is all subjects in the FAS for the given treatment group. This is essentially a NRI approach as subjects who have not achieved the given outcome (whether observed or not) or subjects who discontinue double-blind study treatment are considered as not having responded. Second, the responder rates will be presented for the FAS using Observed Case data. Subjects still on the original double-blind study treatment and with response will be analyzed, with the denominator based on the number of observed values at the given time point.

Continuous other efficacy variables to be analyzed using change from Baseline are:

- BASDAI and BASFI at Weeks 1, 2, 4, 8, 16, 20, 24, 28, 32, 36, 40, 44, 48
- ASDAS at Weeks 2, 4, 8, 12, 16, 20, 24, 28, 32, 36, 40, 44, 48, and 52

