- SI joint SPARCC score <2 at Weeks 12 and 52
- Uveitis flares, IBD exacerbations and Psoriasis exacerbations at Baseline and Weeks 4, 12, 24, 36, 48 and 52 (Summary statistics provided only)
- EQ-5D 5-Item health status at Weeks 4, 12, 24, 36, 48, and 52

For the ‘resource utilization’ variables ‘number of concomitant medical procedures’, ‘number of health care provider consultations not foreseen by the protocol’, ‘number of hospitalizations’, and ‘number of emergency room visits’ descriptive statistics and frequency distributions will be presented for the entire double-blind period.

For the WPS scores, Question 1 responses will be summarized descriptively. Question 2-9 will be summarized by descriptive statistics as well. Treatment comparisons for Question 2 through Question 9 will be performed using a mixed-effect repeated-measures model (MMRM). For each individual question, a separate MMRM will be fitted for the change from baseline, including fixed effects of baseline, treatment, visit, treatment-by-visit interaction and baseline-by-visit interaction, including a random effect of subject and using an unstructured variance-covariance structure. The Kenward-Rogers method will be applied to estimate the denominator degrees of freedom. If convergence problems arise, the covariance structure will be assumed to be autoregressive first order (AR[1]). If that still leads to numerical problems, the more general case, the Toeplitz (TOEP) covariance structure will be used. If all methods above fail to produce a solution, the covariance structure Compound Symmetry (CS) will be used. The least-square means of the treatment difference by visit including 95% confidence intervals and p-values for the test on treatment differences will be summarized.

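### The five 3-level EQ-5D dimensions are sent to a logistic responder analysis with no response or ordinal link defined and no Baseline level in the model

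*SAP*

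**What the plan says.** Section 8.3.1.14 defines the scale: "Each of the 5 health states is divided into 3 levels (no problem, some or moderate problems, and extreme problems", scored 1, 2 and 3. On analysis it says "The 5 dimensions will be analyzed categorically" and nothing more.

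Section 8.3 includes "EQ-5D 5-Item health status at Weeks 4, 12, 24, 36, 48, and 52" in its list of categorical other efficacy variables. For that list, "Categorical other efficacy variables will be analyzed using a logistic regression model with factors of treatment group, region, and MRI/CRP classification". The results are presented in two ways. The first uses all subjects in the FAS: "This is essentially a NRI approach as subjects who have not achieved the given outcome (whether observed or not", with those who discontinue double-blind treatment also counted as not having responded. The second uses observed cases. Section 4.2.3 gives the underlying rule for binary variables: "a subject will be considered a responder only if the response is achieved" and the subject is still on randomized treatment.

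Two entries in the same list are marked as descriptive only: the ASDAS disease-activity states, and the extra-articular events, "Uveitis flares, IBD exacerbations and Psoriasis exacerbations at Baseline and Weeks 4, 12, 24, 36, 48 and 52 (Summary statistics provided only". The EQ-5D entry has no such mark.

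The continuous variables, which include the EQ-5D VAS, are treated differently: "Continuous other efficacy variables will be analyzed using an ANCOVA model including Baseline score as a covariate".

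**The concern.** A responder analysis needs a response, and none is given for the EQ-5D dimensions. Level 1 against 2-3, levels 1-2 against 3, improvement from Baseline, and an ordinal model on all three levels are all compatible with the text. The choice is left to programming, for five dimensions at six visits, with p-values planned.

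The model also makes no use of where the subject started. ASAS20, ASAS40, BASDAI50 and ASDAS-CII compare with Baseline by definition. The EQ-5D level is a raw post-Baseline status, with Baseline in neither the outcome nor the model. The same questionnaire's VAS gets a Baseline-adjusted ANCOVA, and Sections 8.1.3.2 and 8.1.3.3 add Baseline to logistic models in the primary endpoint's sensitivity analyses.

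Subject's health status is one of the other objectives in Section 2.1.3. At stake are the reproducibility and precision of that exploratory comparison. The primary and hierarchical results are not affected.

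**Working it through.** **The plan's own power figure.** The SAP's only power figure is 95% for ASDAS-MI (Section 2.4): 40% against 20%, 150 per arm, two-sided 0.05. With pooled variance:

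- SE under the null = sqrt(2 × 0.30 × 0.70 / 150) = 0.0529
- SE under the alternative = sqrt((0.24 + 0.16) / 150) = 0.0516
- Power = Φ((0.20 − 1.96 × 0.0529) / 0.0516) = 96.9%

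Other variants give 95.9% (continuity-corrected), 96.0% (Fisher exact) and 97.2% (unpooled), so the stated figure is sound. It says nothing about EQ-5D: the SAP gives no level distribution, effect or correlation for that instrument. Everything below rests on assumptions.

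**Set 1.** Assumed: 150 per arm; Baseline levels 10/75/15%; placebo Week 52 levels 25/63/12%; CZP shift 0.35 SD on a latent normal scale; no discontinuation; region and MRI/CRP not modelled; 3000 trials per setting. Power:

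| Baseline to Week 52 correlation | Ordinal, no Baseline | Ordinal + Baseline | Gain (points) | Level 1 vs 2-3, no Baseline | Level 1 vs 2-3 + Baseline |
|---|---|---|---|---|---|
| 0.3 | 74.1% | 76.0% | 1.9 | 63.5% | 64.3% |
| 0.5 | 73.2% | 79.0% | 5.8 | 61.8% | 65.8% |
| 0.6 | 75.1% | 82.7% | 7.6 | 64.7% | 70.5% |
| 0.7 | 74.2% | 85.4% | 11.2 | 63.5% | 72.6% |

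**Set 2.** Same shift and arm size, Baseline levels about 30/60/10%, 500 trials per setting, no discontinuation:

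| Correlation | Ordinal, no Baseline | Ordinal + Baseline | Gain (points) | Level 1 vs 2-3, no Baseline | Levels 1-2 vs 3, no Baseline |
|---|---|---|---|---|---|
| 0.3 | 73.4% | 76.8% | 3.4 | 69.6% | 19.8% |
| 0.5 | 74.6% | 79.4% | 4.8 | 70.8% | 19.2% |
| 0.7 | 72.8% | 84.2% | 11.4 | 67.8% | 22.8% |

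The Monte Carlo standard error of one entry near 75% is sqrt(0.75 × 0.25 / 500) = 1.9 points in Set 2, and 0.8 points with 3000 trials in Set 1.

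**Set 2 with discontinuation.** Assume 30% discontinue on placebo and 15% on CZP, all counted as the worst outcome. At correlations 0.3, 0.5 and 0.7 the ordinal model goes from 97.6 / 97.2 / 97.0% to 98.4 / 98.6 / 98.8% when Baseline is added. The two binary cuts without Baseline both lie between 89% and 92%. Differential discontinuation then carries most of the signal, and both the choice of cut and the Baseline term matter much less.

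**The case against.** Several points on the other side have force.

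- **Frequency tables may have been meant.** Section 3.1 presents categorical data in frequency tables, and the composite rule in Section 4.2.3 is written for binary variables. But Section 8.3 applies the logistic model and the two-way presentation to its whole categorical list, and it uses a descriptive-only mark that EQ-5D lacks. The ambiguity stands, and it needs resolving.
- **The model named need not be binary.** For an ordered 3-level outcome, a logistic regression can be a cumulative-logit model. A reader might infer from Set 1 that the SAP's analysis has 62-65% power against 76-85% for a better one. The documents do not support that: the lower figure belongs to a level 1 split that the SAP never specifies, and the comparison merges two changes. Only the gain from adding Baseline to an ordinal model can fairly be set against the plan's wording.
- **Omitting Baseline is consistent with the primary model.** Section 8.1.2 has no Baseline covariate, and ASAS partial remission and SPARCC below 2 are also unadjusted post-Baseline statuses. This is true, and a reader should not infer that the randomized comparison is invalid without Baseline. Those two variables, however, have a defined dichotomy.
- **Timing.** Section 4.3 has the double-blind outputs produced at the Week 52 lock with treatment codes released, and Sections 2.2.1.3 and 8.1.1 refer to double-blind outputs already produced. A new model now comes after unblinding. This stands and shapes the fix.

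**Conclusion.** The point holds as a specification gap with a better method at hand. The EQ-5D dimensions sit in an inferential responder analysis for which no response or ordinal link is defined, and whose model omits the Baseline level. The SAP does not list the dimensions at Baseline explicitly. That they are available is inferred from the planned change from Baseline in the VAS of the same questionnaire.

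Without discontinuation, adding Baseline to an ordinal model gains about 2 to 11 points of power across correlations 0.3 to 0.7. The gain is small if Baseline is weakly correlated, and under 2 points in the scenario with heavy differential discontinuation. These sizes depend on assumed level frequencies, effect and correlation; only the direction is reasonably secure.

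Section 8.3 declares these p-values nominal, so the consequence is confined to the exploratory health-status objective.

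**What to change.** In Sections 8.3 and 8.3.1.14:

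1. Specify a proportional-odds logistic model on levels 1 to 3 for each dimension, with treatment, region, MRI/CRP classification and the Baseline level of the same dimension. Add a check of proportional odds, and state which data enter this model after double-blind treatment is stopped.
2. For the NRI display, define response as level 1, count discontinuers as not level 1, and include the Baseline level in that model too.
3. Document the rule actually used in the double-blind outputs already produced, and label any re-analysis under items 1 and 2 as post hoc.

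If no inferential comparison was ever intended, the minimum correction is to give EQ-5D the same descriptive-only mark as the other two entries.

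The cost is a few lines of SAP text, a changed model statement and rerun tables, with no new data. The drawbacks are the proportional-odds assumption and the post hoc status of the result.

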### 8.3.1.15 Resources Utilization

The following resource utilization data were collected through UCB standardized modules:

- In-patient hospitalization and emergency room visits
- Health care provider consultations not foreseen by the protocol
- Concurrent medical procedures

Summary statistics and frequency distribution (number of subjects by number of medical resources used) will be presented for resource use with onset during the double-blind period for concurrent medical procedures, health care provider consultations, hospital visits and emergency room (ER) visits. ER visits will be extracted from the hospitalizations/emergency room visit eCRF page (if initial entry point emergency room is ticked).

The categories to be displayed for the frequency distributions of the resource use variables will be defined during the DEM meeting based on blinded data review.

A medical resource is allocated only once in its period of onset, as determined by the (start) date of the event. A resource will be attributed in the same way as an AE is considered a treatment-emergent adverse event (TEAE). The same rules for (partially) missing start and end dates as for AEs will be applied for the resource use.

For the same subject only one hospitalization will be considered if “start date of the second hospitalization - end date of the first hospitalization  $\leq 1$ ”. For missing end dates of hospitalizations (missing discharge dates) the following rules will be applied:

If there is a subsequent hospitalization:

- If the initial entry point and relationship are the same between the two hospitalizations, then the first hospitalization will be grouped with the next one and counted as one hospitalization. In this case the length of the hospitalization will be computed as follows:
  - If the discharge date of the 2nd hospitalization is non-missing, then  
length of stay = 2nd hospitalization discharge date – 1st hospitalization admission date + 1;
  - Else, length of stay = last non missing visit date – 1st hospitalization admission date + 1
- Otherwise, if either the entry point or the relationship of the two hospitalizations is different, then both hospitalizations will be counted as distinct. In this case the length of the 1st hospitalization will be computed as follows:
  - Length of stay = (2nd hospitalization admission date - 1) – 1st hospitalization admission date + 1 (ie, 2nd hospitalization admission date – 1st hospitalization admission date)

In case there is no subsequent hospitalization, then the length of the hospitalization is calculated as length of stay = last non missing visit date – hospitalization admission date + 1

In case of complete consultation date, count only once for a same subject, same consultation date, same location and same provider.

If the procedure name, start date and relationship are the same, then only one procedure is counted, otherwise if at least one variable among procedure name, start date or relationship is different, distinct/several procedures are counted.

If concomitant medical procedures, health care provider consultations not foreseen by the protocol, and hospitalizations/emergency room visits are not available during the study, the respective number variable will be set to 0.

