## **3 DATA ANALYSIS CONSIDERATIONS**

### **3.1 General presentation of summaries and analyses**

All statistical analyses will be performed using SAS® (STATISTICAL ANALYSIS SYSTEM, SAS-Institute, Cary, NC, USA) according to UCB SOPs.

For continuous data in general, summary statistics (n [number of available measurements], arithmetic mean, SD, median, minimum, and maximum) will be presented by treatment group. For selected variables, the first (25th percent) quartile (Q1) and the third (75th percent) quartile (Q3) may also be presented (for patient reported outcomes).

Mean, SD, median and quartiles will be displayed to 1 more decimal place than collected in the source data. Derived variables in general will display the mean, SD and median to 1 more decimal place than the variables used in the derivation (i.e. a change from Baseline will be reported to the same precision as the Baseline data). However, a special rule can be defined as needed for appropriate reporting.

For descriptive statistics of continuous variables by visit, the change from Baseline and actual value at the given time point will be displayed. The change from Baseline is the post-Baseline value minus the Baseline value. If the Baseline or post-Baseline value is missing, then the change from Baseline is set to missing. Percent change from Baseline is the change from Baseline divided by Baseline and multiplied by 100. If the Baseline value is 0 and the post-Baseline value is also 0, then the percent change from Baseline is set to 0. If the Baseline value is 0 and the post-Baseline value is non-zero, then the percent change from Baseline is set to missing. If the Baseline value is missing, the percent change from Baseline is set to missing.

Frequency tables (frequency counts and percentages) will be presented for categorical data. If there are no missing values then the missing row can be removed. If there are missing values (including missing a single assessment or entire visit), then include the missing row with the frequency count and percentage. If there are no subjects in a specific electronic case report form (eCRF) category, then that row will be retained and 0 presented in the table.

In general, percentages will be calculated based on the utilized analysis set. However, in the case of subgroup analyses, the N of the subgroup will be used as denominator.

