### 3.2.1.2 Double-blind treatment period

The double-blind treatment period begins at the Baseline visit (Week 0) at the time of first study medication administration (inclusive) and ends when:

- the subject takes their first dose of open-label CZP (OL-CZP) or open-label other treatment (OL-OT) for those who continue into the SFE or who switch to OL-CZP or OL-OT
- the later of Week 52 visit and last administration of double-blind treatment, for subjects who complete the 52 week main phase of the study and do not continue into the SFE and who do not switch to OL-CZP or OL-OT
- the subject discontinues the study on double-blind treatment prior to the week 52 visit (WD visit) and does not fall into the above categories.

For subjects who prematurely withdraw from the study prior to Week 52 (for example, those who cease to have double-blind and open-label visit data collected), their visit assessments at withdrawal will be assigned to the next scheduled visit following the last visit where assessments are available according to each protocol activity. This could be the next double-blind or open-label visit. All visit measurements, even violating the visit window, will be utilized for the respective visit as long as they are in the proper sequence.

Subjects will be classified as completing the main phase of the study if they complete the Week 52 visit without early withdrawal during the main phase of the study. This is regardless of whether they attend the Follow-up visit or enter SFE period and regardless of whether they are on double-blind treatment, OL-CZP, or OL-OT.

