**Table 11–1: Assignment of Adverse Events to Study Periods**

Type of Subject	Assignment Rule Based on AE Start Date	Assignment
Subjects who do not enter the open-label period and do not enter SFE period	Start date is on or after first study drug administration during the double-blind period and on or before the last study drug administration in the double-blind period + 70 days.	Double-blind TEAE
Subjects who do not enter the open-label period but do enter SFE period	Start date is on or after first study drug administration during the double-blind period and on or before the last study drug administration in the double-blind period + 70 days and prior to the SFE period start	Double-blind TEAE

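### Resource use is summarized by arm as raw per-subject counts over unequal observation windows, so an arm with more early leavers shows fewer resources even at equal true rates

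*SAP*

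**What the plan says.** SAP section 8.3 handles the four resource variables in one sentence: "descriptive statistics and frequency distributions will be presented for the entire double-blind period". Section 8.3.1.15 repeats this at subject level: "Summary statistics and frequency distribution (number of subjects by number of medical resources used) will be presented for resource use with onset during" that period. Under the general rule in section 3.1, summaries "will be presented by treatment group", so the two arms stand side by side. If procedures, consultations or hospital visits "are not available during the study, the respective number variable will be set to 0"; the rule has no condition on how long the subject was observed.

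The window is set elsewhere. For a subject who switches treatment or enters the extension, section 3.2.1.2 ends the double-blind period when "the subject takes their first dose of open-label CZP (OL-CZP) or open-label other treatment (OL-OT"). Section 8.3.1.15 adds: "A resource will be attributed in the same way as an AE is considered a treatment-emergent adverse event (TEAE"). Table 11–1 then admits events "on or before the last study drug administration in the double-blind period + 70 days", but only up to the start of open-label treatment or of the safety follow-up extension (SFE) for subjects who go on to either.

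For adverse events, section 11.2 adds exposure-adjusted incidence and event rates per 100 subject-years. Sections 8.3 and 8.3.1.15 give nothing comparable for resource use.

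**The concern.** A raw count mixes two quantities: how often a subject uses a resource and how long the subject was observed. A subject who switches at Week 16 without an event scores 0, exactly like a subject who completes 52 weeks without one. The counts can be compared across arms only if observation time is similar.

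The SAP gives reason to expect that it is not. Section 8.1.3.2 lets investigators stop study treatment in subjects who do not respond, and section 2.4 expects an ASDAS-MI response of 40% on CZP and 20% on placebo. More and earlier stopping on placebo is therefore plausible. The shorter placebo window would lower the placebo count, and a true advantage of CZP in resource use could look smaller than it is.

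The SAP also treats similar data unevenly. Adverse events, which follow the same attribution rule, are adjusted for exposure, whereas resource counts are not.

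**Working it through.** **The plan's own figures.** The SAP gives no figure for resource use, discontinuation or switching. Its only design figure is 95% power for 40% vs 20% with 150 per arm (section 2.4). A two-proportion calculation gives 96.9% (unpooled variance: 0.20/√((0.24+0.16)/150) = 3.873; 3.873 − 1.960 = 1.913; power 97.2%). That figure is adequate, and the present point does not rest on it.

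**Assumed inputs (not in the documents).** The true rate is 1.0 event per subject-year in both arms. A share d of each arm leaves double-blind treatment at Week x: d = 10% on CZP against 20% to 60% on placebo, or 20% against 50%; x = 16, 26 or 36.

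**Case A: every leaver switches, so the window closes at Week x; completers have 52 weeks.** Mean count per subject = [(1 − d) × 52 + d × x] / 52.

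| CZP / placebo leaving | Week | CZP mean | Placebo mean | Placebo/CZP |
|---|---|---|---|---|
| 10% / 10% | 26 | 0.950 | 0.950 | 1.00 |
| 10% / 20% | 36 | (46.8 + 3.6)/52 = 0.969 | (41.6 + 7.2)/52 = 0.938 | 0.97 |
| 10% / 40% | 26 | (46.8 + 2.6)/52 = 0.950 | (31.2 + 10.4)/52 = 0.800 | 0.84 |
| 20% / 50% | 26 | (41.6 + 5.2)/52 = 0.900 | (26 + 13)/52 = 0.750 | 0.83 |
| 10% / 60% | 16 | (46.8 + 1.6)/52 = 0.931 | (20.8 + 9.6)/52 = 0.585 | 0.63 |

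Over all scenarios with unequal leaving, the ratio is 0.63 to 0.97 although the true ratio is 1.00. The frequency distribution shifts too. With Poisson counts at 10%/40% and Week 26, the share with zero use is 0.9e^(−1) + 0.1e^(−0.5) = 39% on CZP and 0.6e^(−1) + 0.4e^(−0.5) = 46% on placebo.

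**Case B: no leaver switches, so the 70-day tail applies.** Leavers have x + 10 weeks. Completers have their last dose at Week 50, hence 60 weeks.

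- 10%/20%, Week 36: (48 + 9.2)/(54 + 4.6) = 57.2/58.6 = 0.98
- 10%/40%, Week 26: (36 + 14.4)/(54 + 3.6) = 50.4/57.6 = 0.875
- 10%/60%, Week 16: (24 + 15.6)/(54 + 2.6) = 39.6/56.6 = 0.70

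The range is 0.70 to 0.98. If completers instead roll straight into the extension, their window stays near 52 weeks and the gap narrows further. At 10%/40% and Week 26 it is (31.2 + 14.4)/(46.8 + 3.6) = 45.6/50.4 = 0.90.

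**Rates over the matching window.** In Case A at 10%/40% and Week 26, 0.950 events over 0.950 years and 0.800 events over 0.800 years both give 100 per 100 subject-years. The ratio is 1.00 in every scenario.

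**Rates over the wrong window.** Take leavers at Week 16 who do not switch, 40% on placebo and 15% on CZP, with events counted over the tail but divided by double-blind time alone.

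- Placebo: (0.6 × 60 + 0.4 × 26)/(0.6 × 52 + 0.4 × 16) = 46.4/37.6 = 1.234
- CZP: (0.85 × 60 + 0.15 × 26)/(0.85 × 52 + 0.15 × 16) = 54.9/46.6 = 1.178
- Ratio: 1.234/1.178 = 1.05, a spurious placebo excess of about 5%

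The choice of denominator therefore matters.

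**The case against.** The other side has several good arguments.

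- **No formal comparison.** Section 8.3 plans treatment comparisons with confidence intervals and p-values for the Work Productivity Survey but only descriptive output for resource use. These variables lie outside the testing hierarchy. A reader might infer that the plan runs a biased test or shows one arm to be cheaper. It does neither: there is no test, and no cost is computed.
- **80% and 60% are not switching rates.** A reader might take the complement of the expected response rates as the share who switch. Those are expected Week 52 failures on a demanding response definition, and section 8.1 already counts discontinuers among them. They support a direction, not a size.
- **Direction is not guaranteed.** Subjects may use more care just before leaving, which raises their count and can offset the lost time. A reader might expect the ordering of the arms to reverse. Nothing in the SAP shows this.
- **Scoring 0 is not an error.** On event forms, no record means no event. Setting the number to 0 ("the respective number variable will be set to 0") is needed for a rate as well. The problem is the missing time beside the count.
- **The 70-day tail helps.** It does so, as Case B shows, without removing the effect.
- **Readers can see unequal follow-up.** Exposure (section 11.1) and discontinuation (section 5.1) are reported by arm. This warns the reader but does not correct the resource table.

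None of these supplies a time adjustment for the counts.

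**Conclusion.** The point holds as a limited one. The resource-use summaries are unadjusted counts over windows that are shorter for early leavers, and nothing in the SAP corrects them. With equal true rates, the arm with more leavers shows about 3% to 37% fewer events per subject if leavers switch, and 2% to 30% fewer if none switches and completers are observed for 60 weeks. With equal leaving and equal exit times there is no distortion.

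These ranges rest on assumed discontinuation shares, exit weeks and a constant rate of use. They are not estimates for this trial. The primary endpoint and the tested secondary endpoints are unaffected. This is an inexpensive improvement to an exploratory descriptive table.

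**What to change.** In sections 8.3 and 8.3.1.15, beside the counts, report each resource by arm as events per 100 subject-years, with a 95% CI that is robust to overdispersion and with mean observation time, in parallel with the exposure-adjusted event rate in section 11.2. Keep the frequency distribution as supportive.

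Define the denominator as the window that attributes the resource: from the first double-blind dose to the last double-blind dose + 70 days, cut at the start of open-label treatment or of the SFE period, and at death or last contact. Double-blind time alone does not match this window. Nor do exposure methods 2 and 3 in section 11.1 as written: method 2 adds 14 days; method 3 adds 70 days but subtracts long drug holidays; neither states a cut at open-label or SFE start.

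The cost is one derived denominator and added columns, from dates that adverse event assignment already uses. Section 4.3 places the double-blind outputs at the Week 52 lock, and section 8.1.1 says that double-blind outputs have already been produced. Added now, the rates would be a supplementary re-run after unblinding and should be labelled so.
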